2.4 Immune Biomarkers

Immunologic evaluations will include PD-L1 expression, type of antitumor immune response and stability of T cell activation before and after treatment. Tissue slides will be used to assess PDL1 expression and TIL composition/distribution before treatment using multicolor imaging. The frequency of tumor infiltrating T cells as well as the expression level of inhibitor molecule PDL-1 on the tumors has been associated with efficacy of PD1 blocking therapy. [50-52](#)

Peripheral blood mononuclear cells (PBMC) will be assessed for composition of CD4 and CD8 T cells; naïve and memory cells (CD45RO/RA, CCR7), recently activated T cells (HLADR, CD38, Nur77, Ki67), the frequency of T cells with an exhausted phenotype (PD-1, Lag-3, Tim3, CD244), and regulatory phenotype (CD25, FoxP3). It is well established that tumors suppress the immune system and promote the development of immune cells with immune suppressive and tumor promoting capacities including myeloid-derived suppressor cells (MDSC) that directly inhibit cytolytic CD8 T cell proliferation/function and promote angiogenesis and metastases and Tregs that can directly suppress CD8 T cells. In addition, CD8 T cells associated with tumor environments often express a dysfunctional and exhausted phenotype that we aim to overcome with PD1 blocking therapy. Longitudinal assessment of the patients' immune status could provide important clues on the immune mechanisms that may affect immunotherapy efficacy. [53-55](#)

2.5 Dosing Rationale

2.5.1 Axitinib

2.5.1.1 Adult patients (≥ 18 years of age)

Available data presented above have demonstrated the safety of administering antiangiogenic therapy and PD1 inhibitor therapy in combination to patients with adult RCC at each agent's recommended phase 2 dose (RP2D). In addition, per the axitinib package insert, based on available published data, it has become an accepted standard to dose increase adults with RCC amenable to dose titration upwards beyond 5 mg PO BID. This is an acceptable standard and will be permitted on trial (see [Section 4.3.3](#) and [Section 4.4.3](#)).

2.5.1.2 Pediatric patients (< 18 years of age)

Available data (study ADVL1315) noted above has established the RP2D for axitinib as 2.4 mg/m²/dose (maximum of 5 mg/dose) PO BID. [49](#) Dose titration will be permitted in patients < 18 years of age on this trial (see [Sections 4.3.3, 4.4.3](#), and [Appendix IV](#)).

2.5.2 Nivolumab

2.5.2.1 Adult patients (≥ 18 years of age)

A fixed nivolumab FDA Approved dose of 240 mg IV every 2 weeks or 480 mg IV every 4 weeks will be used for adult patients.

With Amendment #5, adults will have the option to receive nivolumab on one of the above mentioned schedules as both are FDA approved and felt equivalent with regards to efficacy in adult patients.

2.5.2.2 Pediatric patients (< 18 years of age)

The recommended nivolumab dose of 3 mg/kg (up to a maximum dose of 240 mg) IV every 2 weeks will be used for pediatric patients.

2.6 Rationale for Cross-Over Design (Effective with Amendment 5A)

For patients who progress on Arm C (nivolumab monotherapy), evolving clinical options include simple 'continuing beyond progression', change to anti-VEGF TKI-based therapy, or the addition of anti-VEGF TKI-based therapy. The concept of continuing on PD1 inhibitor-based therapy beyond progressive disease, which at times occurs in the setting of mixed responses, has been formally investigated in multiple cancers including renal cell carcinoma.⁵⁶⁻⁵⁹ Available data suggest that continuing such therapy is both safe, and at times, efficacious^{57, 58} with potential improvements noted in overall survival.⁵⁹ That said, either switching to or adding an anti-VEGF TKI-based therapy can be effective in some RCC variants.⁶⁰ Considering existing standards in management of RCC and the goals of this trial, cross-over from Arm C (nivolumab monotherapy) to Arm A (combination nivolumab/axitinib therapy) will be permitted for patients on Arm C at first disease progression. Data that results from such cross-over will not impact the primary aim of the study, but will contribute to our understanding of tRCC patient clinical tolerance and response to such therapies, survival outcomes, and pharmacokinetics of axitinib in pediatric patients treated with combination therapy.

2.7 Pharmacokinetics Studies (Effective with Amendment 5A)

COG study ADVL1315 described the phase 1 experience of axitinib in children with relapse/refractory solid tumors, including pharmacokinetic parameters.⁴⁹ While helpful, such data remains limited. The FDA has requested that additional PK be obtained in children randomized to Arm A (axitinib/nivolumab) where they are treated with axitinib on study AREN1721 to further characterize the PK specifically in children and adolescents with TFE RCC treated with concurrent nivolumab (a combination for which no PK for axitinib is currently available). AREN1721 also permits the option for axitinib dose escalation beyond doses used in ADVL1315. Such PK data will be used to help define future guidelines of use for axitinib in the pediatric population.

3.0 STUDY ENROLLMENT PROCEDURES AND PATIENT ELIGIBILITY

3.1 Study Enrollment

3.1.1 Patient Registration

Prior to enrollment on this study, patients must be assigned a COG patient ID number. This number is obtained via the Patient Registry module in OPEN once authorization for the release of protected health information (PHI) has been obtained. The COG patient ID number is used to identify the patient in all future interactions with COG. If you have problems with the registration, please refer to the online help. For additional help or information, please contact the CTSU Help Desk at [name] or [contact].

A Biopathology Center (BPC) number will be assigned as part of the registration process. Each patient will be assigned only one BPC number per COG Patient ID.

For additional information about the labeling of specimens please refer to the Pathology and/or Biology Guidelines in this protocol.

Please see [Appendix I](#) for detailed CTEP Registration Procedures for Investigators and Associates, and Cancer Trials Support Unit (CTSU) Registration Procedures including: how to download site registration documents; requirements for site registration, submission of regulatory documents and how to check your site's registration status.

NOTE: In order for an institution to maintain COG membership requirements, every patient with a known or suspected neoplasm needs to be offered participation in APEC14B1, *Project: Every Child A Registry, Eligibility Screening, Biology and Outcome Study*.

3.1.2 IRB Approval

Each investigator or group of investigators at a clinical site must obtain IRB approval for this protocol and submit IRB approval and supporting documentation to the CTSU Regulatory Office before they can be approved to enroll patients. For CTEP and Division of Cancer Prevention (DCP) studies open to the National Clinical Trials Network (NCTN) and NCI Community Oncology Research Program (NCORP) Research Bases after March 1, 2019, all U.S.-based sites must be members of the NCI Central Institutional Review Board (NCI CIRB). In addition, U.S.-based sites must accept the NCI CIRB review to activate new studies at the site after March 1, 2019. Local IRB review will continue to be accepted for studies that are not reviewed by the CIRB, or if the study was previously open at the site under the local IRB. International sites should continue to submit Research Ethics Board (REB) approval to the CTSU Regulatory Office following country-specific regulations.

Sites participating with the NCI CIRB must submit the Study Specific Worksheet for Local Context (SSW) to the CIRB using IRBManager to indicate their intent to open the study locally. The NCI CIRB's approval of the SSW is automatically communicated to the CTSU Regulatory Office, but sites are required to contact the CTSU Regulatory Office at [contact] to establish site preferences for applying NCI CIRB approvals across their Signatory Network. Site preferences can be set at the network or protocol level. Questions about establishing site preferences can be addressed to the CTSU Regulatory Office by email or calling [name].

Sites using their local IRB or REB, must submit their approval to the CTSU Regulatory Office using the Regulatory Submission Portal located in the Regulatory section of the CTSU website. Acceptable documentation of local IRB/REB approval includes:

- Local IRB documentation;
- IRB-signed CTSU IRB Certification Form; and/or
- Protocol of Human Subjects Assurance Identification/IRB Certification/Declaration of Exemption Form.

In addition, the Site-Protocol Principal Investigator (PI) (i.e. the investigator on the IRB/REB approval) must meet the following criteria in order for the processing of the IRB/REB approval record to be completed:

- Holds an active CTEP status;
- Rostered at the site on the IRB/REB approval (*applies to US and Canadian sites only*) and on at least one participating roster;
- If using NCI CIRB, rostered on the NCI CIRB Signatory record;
- Includes the IRB number of the IRB providing approval in the Form FDA 1572 in the RCR profile; and
- Holds the appropriate CTEP registration type for the protocol.

Additional Requirements

Additional requirements to obtain an approved site registration status include:

- An active Federal Wide Assurance (FWA) number;
- An active roster affiliation with the Lead Protocol Organization (LPO) or a Participating Organization (PO); and
- Compliance with all protocol-specific requirements (PSRs).

For information about the submission of IRB/REB approval documents and other regulatory documents as well as checking the status of study center registration packets, please see [Appendix I](#).

Institutions with patients waiting that are unable to use the Portal should alert the CTSU Regulatory Office immediately at [name] in order to receive further instruction and support. For general (non-regulatory) questions call the CTSU General Helpdesk at: [name].

Note: Sites participating on the NCI CIRB initiative and accepting CIRB approval for the study are not required to submit separate IRB approval documentation to the CTSU Regulatory Office for initial, continuing or amendment review.

3.1.3 Reservation Requirements

Prior to obtaining informed consent and enrolling a patient, a reservation must be made following the steps below. Reservations may be obtained 24 hours a day through the Oncology Patient Enrollment Network (OPEN) system. Patients must be enrolled within 5 calendar days of making a reservation.

Note: As of Amendment 5A, each time a reservation is made for a pediatric patient, sites should order a sample collection kit for required pharmacokinetic studies. This is to ensure timely receipt of the kit in the event the pediatric patient is randomized to Arm A, and to ensure a kit is readily available in the event that a patient randomized to Arm C should cross-over to Arm A. See [Section 15.1](#) for complete details.

Patient enrollment for this study will be facilitated using the Slot-Reservation System in conjunction with the registration system in OPEN. Prior to discussing protocol entry with the patient, all site staff must use the CTSU OPEN Slot Reservation System to ensure that a slot on the protocol is available to the patient. Once a slot reservation confirmation is obtained, site staff may then proceed to enroll the patient to this study.

If the study is active, a reservation can be made by following the steps below:

- 1) Log in to <https://open.ctsu.org/open/> using your CTEP IAM user name and password.
- 2) In order to make a reservation, the patient must have an OPEN patient number. Click on the 'Slot Reservation' tab to create an OPEN patient number, under 'Patients'.
- 3) Using the OPEN patient number '**RESERVE**' a slot for that patient.
- 4) On the 'Create Slot Reservation' page, select the Protocol Number, enter the COG Patient ID, and choose the required stratum (if applicable) in order to obtain a reservation.

Refer to the 'Slot Reservation Site User Guide' posted under the 'Help' tab in OPEN for detailed instructions:

https://www.ctsu.org/open/Site_Resources/Training/Users_Manual/CTSU-OPEN-SlotReservationSiteUserGuide.pdf

3.1.4 Study Enrollment

Patient enrollment will be facilitated using the Oncology Patient Enrollment Network (OPEN). OPEN is a web-based registration system available on a 24/7 basis. OPEN is integrated with CTSU regulatory and roster data and with the Lead Protocol Organization (LPOs) registration/randomization systems or the Theradex Interactive Web Response System (IWRS) for retrieval of patient registration/randomization assignment. OPEN will populate the patient enrollment data in NCI's clinical data management system, Medidata Rave.

Requirements for OPEN access:

- A valid CTEP-IAM account;
- To perform enrollments or request slot reservations: Must be on an LPO roster, ETCTN corresponding roster, or participating organization roster with the role of Registrar. Registrars must hold a minimum of an Associate Plus (AP) registration type;
- If a Delegation of Tasks Log (DTL) is required for the study, the registrars must hold the OPEN Registrar task on the DTL for the site; and
- Have an approved site registration for the protocol prior to patient enrollment.

To assign an Investigator (IVR) or Non-Physician Investigator (NPIVR) as the treating, crediting, consenting, drug shipment (IVR only), or receiving investigator for a patient transfer in OPEN, the IVR or NPIVR must list the IRB number used on the site's IRB approval on their Form FDA 1572 in RCR. If a DTL is required for the study, the IVR or NPIVR must be assigned the appropriate OPEN-related tasks on the DTL.

Prior to accessing OPEN, site staff should verify the following:

- Patient has met all eligibility criteria within the protocol stated timeframes; and
- All patients have signed an appropriate consent form and HIPAA authorization form (if applicable).

Note: The OPEN system will provide the site with a printable confirmation of registration and treatment information. You may print this confirmation for your records.

Access OPEN at <https://open.ctsu.org> or from the OPEN link on the CTSU members' website. Further instructional information is in the OPEN section of the CTSU website at <https://www.ctsu.org> or <https://open.ctsu.org>. For any additional questions, contact the CTSU Help Desk at [name] or [contact].

3.1.5 Timing

Patients must be enrolled before treatment begins. The date protocol therapy is projected to start must be no later than **five (5)** calendar days after the date of study enrollment. **Patients who are started on protocol therapy on a phase 2 study prior to study enrollment will be considered ineligible.**

All clinical and laboratory studies to determine eligibility must be performed within 7 days prior to enrollment unless otherwise indicated in the eligibility section below.

3.2 Patient Eligibility Criteria

Important note: The eligibility criteria listed below are interpreted literally and cannot be waived. All clinical and laboratory data required for determining eligibility of a patient enrolled on this trial must be available in the patient's medical/research record which will serve as the source document for verification at the time of audit.

All clinical and laboratory studies to determine eligibility must be performed within 7 days prior to enrollment unless otherwise indicated. Laboratory values used to assess eligibility must be no older than seven (7) days at the start of therapy. Laboratory tests need not be repeated if therapy starts within seven (7) days of obtaining labs to assess eligibility. If a post-enrollment lab value is outside the limits of eligibility, or laboratory values are > 7 days old, then the following laboratory evaluations must be re-checked within 48 hours prior to initiating therapy: CBC with differential, bilirubin, ALT (SGPT), and serum creatinine. If the recheck is outside the limits of eligibility, the patient may not receive protocol therapy and will be considered off protocol therapy.

Imaging studies, if applicable, must be obtained within 4 weeks prior to enrollment and start of protocol therapy (repeat the tumor imaging if necessary).

Echocardiogram, must be obtained within 8 weeks prior to enrollment and start of protocol therapy (repeat echocardiogram if necessary).

3.2.1 Age

Patients must be \geq 12 months at enrollment.

3.2.2 Body Surface Area (BSA)

Patients must have a Body Surface Area (BSA) $\geq 0.53 \text{ m}^2$.

3.2.3 Diagnosis

Histologically confirmed unresectable or metastatic translocation morphology renal cell carcinoma diagnosed using WHO-defined criteria. Patients may be newly diagnosed or have received prior cancer therapy.

3.2.3.1 Patients must have had histologic verification of the malignancy.

3.2.3.2 Patients must have measurable disease, documented by clinical, radiographic, or histologic criteria as defined by RECIST v1.1.

3.2.3.3 Patients must have a tumor showing the appropriate morphologic appearance, and either confirmed TFE3 nuclear protein expression by immunohistochemistry with appropriate positive and negative controls performed at a CLIA-certified laboratory, or evidence of TFE3 or TFEb translocation by either FISH or RT-PCR performed at a CLIA-certified laboratory. For TFE3 immunohistochemistry, any nuclear positivity in the presence of appropriate positive and negative controls should be considered as evidence of TFE3 immunohistochemical expression.

NOTE: If the institution is unable to perform these studies, unstained slides may be submitted to [name], who will perform TFE3 analysis at no charge. The slide will be returned to the referring institution for local evaluation, to be included in their institutional report. See [Section 14.1.2](#) for complete details.

3.2.4 Performance Level

Patients must have a performance status corresponding to ECOG scores of 0, 1 or 2. Use Karnofsky for patients > 16 years of age and Lansky for patients ≤ 16 years of age. See [Appendix II](#).

3.2.5 Life Expectancy

Patients must have a life expectancy of ≥ 8 weeks.

3.2.6 Prior Therapy

Patients must have fully recovered from the acute toxic effects of all prior chemotherapy, immunotherapy, or radiotherapy prior to entering this study.

- a. Myelosuppressive chemotherapy: Must not have received within 2 weeks of entry onto this study (6 weeks if prior nitrosourea).
- b. Immunotherapy: Must not have received within 4 weeks of entry onto this study.
- c. Biologic (anti-neoplastic agent): At least 7 days since the completion of therapy with a biologic agent.
- d. Radiation therapy (RT): ≥ 2 weeks for local palliative RT (small port); ≥ 6 months must have elapsed if prior craniospinal RT or if $\geq 50\%$

radiation of pelvis; ≥ 6 weeks must have elapsed if other substantial BM radiation.

3.2.7 Organ Function Requirements

3.2.7.1 Adequate Bone Marrow Function Defined As:

- Peripheral absolute neutrophil count (ANC) $\geq 1000/\mu\text{L}$
- Platelet count $\geq 75,000/\mu\text{L}$ (transfusion independent)
- Hemoglobin $\geq 8.0 \text{ g/dL}$ (may receive RBC transfusions)

3.2.7.2 Adequate Renal Function Defined As:

- Urine protein: $\leq 30 \text{ mg/dL}$ in urinalysis or $\leq 1+$ on dipstick, unless quantitative protein is $< 1000 \text{ mg}$ in a 24 h urine sample.
- **For patients < 18 years of age:** Serum creatinine $\leq 1.5 \times$ upper limit of normal (ULN), or measured or calculated* creatinine clearance or radioisotope GFR $\geq 60 \text{ mL/min}/1.73 \text{ m}^2$ for patient with creatinine levels $> 1.5 \times$ institutional ULN, or a serum creatinine based on age/gender as follows:

Age	Maximum Serum Creatinine (mg/dL)	
	Male	Female
1 to < 2 years	0.6	0.6
2 to < 6 years	0.8	0.8
6 to < 10 years	1	1
10 to < 13 years	1.2	1.2
13 to < 16 years	1.5	1.4
≥ 16 years	1.7	1.4

The threshold creatinine values in this table were derived from the Schwartz formula for estimating GFR utilizing child length and stature data published by the CDC.⁶¹

- **For patients ≥ 18 years of age:** Serum creatinine $\leq 2 \times$ ULN, or measured or calculated* creatinine clearance or radioisotope GFR $\geq 40 \text{ mL/min}/1.73 \text{ m}^2$ for patient with creatinine levels $> 2 \times$ institutional ULN.

*Creatinine clearance should be calculated per institutional standard.

3.2.7.3 Adequate Liver Function Defined As:

- Serum total bilirubin $\leq 1.5 \times$ ULN for age, or direct bilirubin \leq ULN for patients with total bilirubin levels $> 1.5 \times$ ULN.
- SGOT (AST) or SGPT (ALT) $< 3 \times$ ULN for age.
- Albumin $> 2.5 \text{ mg/dL}$.

3.2.7.4 Adequate Cardiac Function Defined As:

- Shortening fraction of $\geq 27\%$ by echocardiogram, or
- Ejection fraction of $\geq 50\%$ by radionuclide angiogram.
- No history of myocardial infarction, severe or unstable angina, or peripheral vascular disease.
- QTc ≤ 480 msec. Note: Patients with Grade 1 prolonged QTc (450-480 msec) at the time of study enrollment should have

correctable causes of prolonged QTc addressed if possible (i.e., electrolytes, medications).

3.2.7.5 Adequate Coagulation Function Defined As:

- International Normalized Ratio (INR) or Prothrombin Time (PT) $\leq 1.5 \times$ ULN. However, if patient is receiving anticoagulant therapy, PT or PTT should be within therapeutic range of intended use of anticoagulants.
- Activated Partial Thromboplastin Time (aPTT) $\leq 1.5 \times$ ULN unless patient is receiving anticoagulant therapy as long as PT or PTT is within therapeutic range of intended use of anticoagulants.

3.2.7.6 Adequate Blood Pressure Control Defined As:

- A baseline blood pressure (BP) \leq the 95th percentile for age, height, and gender for patients < 18 years old (see [Appendix III](#)), or ≤ 150 mmHg (systolic) and ≤ 90 mmHg (diastolic) for patients ≥ 18 years old.

Note: 2 serial blood pressures should be taken at least 1 hour apart and averaged to determine baseline BP (see [Section 5.2.5.1](#)).

- Patients are eligible if on stable doses (≥ 7 days) of anti-hypertensive medications with a baseline BP meeting the criteria above.

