3.2.8.3 Prior Therapy

- Patients who have received prior therapy with axitinib, nivolumab, or other PD1/PD-L1 targeted therapies.
- Patients who have received prior therapy with more than one anti-VEGF based agent (antibody or tyrosine kinase inhibitor).
- Patients with hypersensitivity to axitinib, nivolumab, or any of its excipients.
- Patients who previously received an allogeneic stem cell transplant (SCT) or solid organ transplant are not eligible.
- Patients may not be receiving any other investigational agents (within 4 weeks prior to study enrollment).
- Patients who have received prior anti-cancer monoclonal antibody (mAb) within 4 weeks prior to study enrollment or who have not recovered (i.e., \leq Grade 1 or at baseline) from adverse events due to agents administered more than 4 weeks prior to enrollment.
- Surgery: Patients who have had or who are planning to have the following invasive procedures are not eligible:
 - o Major surgical procedure, laparoscopic procedure, open biopsy, core biopsy, fine needle aspirate, or significant traumatic injury within 7 days prior to enrollment. **NOTE:** External central lines must be placed at least 3 days prior to

planned treatment initiation and subcutaneous ports must be placed at least 7 days prior to planned treatment initiation.

- Patients who are planning cytoreductive surgery within the first 12 weeks following therapy initiation.
- Patients who have a serious or non-healing wound or ulcer at the time of study enrollment are not eligible.
- Patients who have a history of abdominal fistula, gastrointestinal perforation, or intra-abdominal abscess within 28 days of study enrollment are not eligible.
- Patients who have received prior targeted small molecule therapy within 2 weeks of enrollment or have not recovered (i.e., \leq Grade 1 or at baseline) from adverse events due to agents administered more than 4 weeks prior to enrollment. **NOTE:** Subjects with \leq Grade 2 neuropathy are an exception to this criterion and may qualify for the study.

3.2.8.4 Pre-existing conditions, which may include:

- Additional known malignancy that is progressing or requires active treatment. Exceptions include basal cell carcinoma of the skin, or squamous cell carcinoma of the skin that has undergone potentially curative therapy, or *in situ* cervical cancer.
- Patients with underlying immune deficiency, chronic infections including hepatitis, tuberculosis (TB), or autoimmune disease.

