- HIV-infected patients with the exception of patients on an effective anti-retroviral therapy with an undetectable viral load within 6 months prior to enrollment.
- Patients with underlying hematologic issues including congenital bleeding diathesis, known previous GI bleeding requiring intervention within the past 6 months, history of hemoptysis within 42 days prior to study enrollment, active pulmonary emboli, or deep vein thromboses (DVT) that are not stable on anticoagulation regimen.
- Patients must not have had significant vascular disease (i.e. Moya-Moya, aortic aneurysm requiring surgical repair).
- A known history of, or any evidence of active, non-infectious pneumonitis.
- Patients with known active central nervous system (CNS) metastases and/or carcinomatous meningitis or leptomeningeal disease. Patients with previously treated brain metastases may participate provided they are stable (without evidence of progression by imaging for at least 4 weeks prior to study enrollment and any neurologic symptoms have returned to baseline), have no evidence of new or enlarging brain metastases, and are not using steroids for at least 7 days prior to study enrollment. This exception does not include carcinomatous meningitis which is excluded regardless of clinical stability.
- Any uncontrolled, intercurrent illness including but not limited to ongoing or active infection, symptomatic congestive heart failure, unstable angina pectoris, cardiac arrhythmia.

- Any serious medical or psychiatric illness/condition including substance use disorders likely in the judgment of the Investigator(s) to interfere or limit compliance with study requirements/treatment.
- Patients with active autoimmune disease that has required systemic treatment in the past 2 years (i.e. with use of disease modifying agents, corticosteroids or immunosuppressive drugs). Replacement therapy (e.g., thyroxine, insulin, or physiologic corticosteroid replacement therapy for adrenal or pituitary insufficiency, etc.) is not considered a form of systemic treatment.

3.2.8.5 Treatments and/or medications the patient is receiving or has received that would make her/him ineligible, including:

- Concomitant (or receipt of) treatment with medications that may affect the metabolism of nivolumab and/or axitinib within 7 days prior to planned first dose of protocol therapy.

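### The printed albumin limit, in mg/dL, cannot exclude anyone; secondarily, an unqualified autoimmune exclusion leaves a later, narrower bullet without effect

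*Combined protocol and SAP*

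**What the plan says.** Section 3.2 opens with a general rule: "The eligibility criteria listed below are interpreted literally and cannot be waived". It adds that the supporting data must be on file for verification at audit.

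Section 3.2.7.3 lists three liver-function criteria: bilirubin, AST or ALT, and "Albumin $> 2.5 \text{ mg/dL". In the same organ-function section the hemoglobin limit is "Hemoglobin $\geq 8.0 \text{ g/dL". No other part of the document gives an albumin limit or unit; the observation lists in Sections 4.3.2, 4.4.2 and 4.5.2 and the table in Section 7.1 name albumin only as a test to be done.

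Section 3.2.8.4 mentions autoimmune disease in two separate exclusion bullets. The first reads "Patients with underlying immune deficiency, chronic infections including hepatitis, tuberculosis (TB), or autoimmune disease". The later one reads "Patients with active autoimmune disease that has required systemic treatment in the past 2 years", and goes on to say that replacement therapy, such as thyroxine or insulin, "is not considered a form of systemic treatment". Nothing links the two bullets or says which governs.

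**The concern.** Serum albumin is of the order of grams per decilitre, so a limit of 2.5 milligrams per decilitre is one that no patient could fail. In most protocols a site would quietly read the unit it expects. Here the criteria are declared literal and non-waivable, so a site that turns a patient away on a presumed g/dL limit applies a rule the protocol does not contain, while a site that follows the text has no albumin check at all. The re-check before treatment described in Section 3.2 does not close the gap: it covers blood counts, bilirubin, ALT and creatinine, but not albumin.

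The autoimmune wording is a lesser matter of the same kind. The later bullet carries three deliberate qualifiers (active disease, a two-year window, and a carve-out for replacement therapy) that have no work to do if the earlier bullet already excludes all autoimmune disease. A site reading the later bullet may reasonably wonder whether some of these patients were meant to enter.

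At stake are the content of the screening rules, consistency between sites and the audit trail. The sample-size calculation is not at stake.

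**Working it through.** **Albumin.** Inputs: the printed limit of 2.5 mg/dL (Section 3.2.7.3), the conversion 1 g = 1000 mg, and an assumed serum albumin range of 1.0 to 5.0 g/dL. The range is not in the documents and is deliberately wide.

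1. Printed limit in g/dL: 2.5 / 1000 = 0.0025 g/dL.
2. Ratio of a patient's value to the limit = (albumin in g/dL × 1000) / 2.5.

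| Albumin (g/dL) | mg/dL | Multiple of printed limit | Passes as printed | Would pass > 2.5 g/dL (assumed unit) |
|---|---|---|---|---|
| 1.0 | 1000 | 400 | yes | no |
| 1.5 | 1500 | 600 | yes | no |
| 2.0 | 2000 | 800 | yes | no |
| 2.5 | 2500 | 1000 | yes | no |
| 3.5 | 3500 | 1400 | yes | yes |
| 5.0 | 5000 | 2000 | yes | yes |

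3. Every value in the range passes as printed. If g/dL was intended, the limit would be 2500 mg/dL, and 2500 / 2.5 = 1000, so the printed figure is 1000-fold too low.
4. Could the unit be an artefact of reading the PDF? This cannot be fully excluded. However, Section 3.2.7 shows hemoglobin in g/dL and urine protein and creatinine in mg/dL, so the two units came through distinctly. An artefact is unlikely.

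**Autoimmune disease.** No arithmetic applies. Setting the two bullets of Section 3.2.8.4 against four kinds of patient:

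| Patient | Earlier, unqualified bullet | Later, qualified bullet |
|---|---|---|
| Inactive disease, no systemic treatment in 2 years | excluded | not excluded |
| Active disease, no systemic treatment in 2 years | excluded | not excluded |
| Active disease, replacement therapy only | excluded | not excluded |
| Active disease, systemic treatment in 2 years | excluded | excluded |

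The bullets have different scope in three of the four rows. Both are exclusions, and neither says that a patient outside it is eligible. Applied together, they exclude all four rows. The later bullet adds nobody, and its qualifiers change no decision.

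**The case against.** The best reply on albumin is that this is an obvious unit slip which any site would read through, and that nothing in the document shows a patient entering because of it. That is fair as to likely practice, but it relies on sites departing from a text they are told to take literally. It also does not say whether 2.5 is the intended number once the unit is changed.

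A reader might infer that liver screening as a whole has failed. The documents do not support that: the bilirubin and AST/ALT limits in Section 3.2.7.3 and the INR/PT limit in Section 3.2.7.5 still work. Nor does the protocol give a reason for the albumin limit. Section 6.1 describes axitinib as highly protein-bound and eliminated mainly by the hepatobiliary route, but tying the criterion to that is inference, and Arm C patients receive axitinib only if they cross over.

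On the autoimmune bullets, the reply is that two exclusions of different width form a redundancy with one determinate result. That stands. A reader might infer that the text gives two literally opposite answers for the same patient. It does not; the broader exclusion prevails. What survives is that the qualifiers are idle, which points to a possible difference between intent and text.

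A reader might also look for an effect on power or sample size. One patient is 1/28 = 3.6% of the target, but that measures no effect: the number of disputed patients is unknown, and someone turned away at screening does not use up a place. The 5% allowance in Section 9.1 is illustrated by Arm B assignment and central pathology problems, not by disputes of this kind. Section 9.4 treats randomized patients with centrally confirmed tRCC, Arm B aside, as evaluable for PFS. A patient enrolled against either criterion would therefore apparently stay in the primary comparison.

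**Conclusion.** The albumin point holds. As printed, one of the three criteria in Section 3.2.7.3 cannot exclude anyone, and the rule that criteria are literal and non-waivable makes this a wrong enrolment threshold, more than a cosmetic slip. Its size is a factor of 1000 if g/dL was meant. The documents do not state that unit, so it remains an assumption. The conclusion that nobody is screened out rests only on serum albumin being far above 0.0025 g/dL.

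The autoimmune point holds as a secondary inconsistency: the earlier bullet makes the later one's qualifiers inoperative, a narrower rule may have been intended, and sites may be confused.

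Neither point alters the target of 28 patients, the 22 PFS events, the one-sided alpha of 0.15 or the 80% power. Both should be corrected because they sit among criteria that sites may not interpret or waive.

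**What to change.** 1. **Section 3.2.7.3.** The sponsor confirms the intended albumin threshold and prints it with the correct unit. This is a one-line change. If it results in a limit that patients can fail, some patients who pass the present text would no longer be eligible, so the change should be made by amendment with a clear effective date.
2. **Section 3.2.8.4.** The sponsor reconciles the two autoimmune bullets into a single rule of its choosing. If the broad exclusion is kept, deleting the idle bullet leaves the literal population as it is. If the narrower wording is kept, the literal eligible population widens partway through the trial. That is a substantive amendment and should be described as such, with the date, so that patients enrolled before and after can be distinguished in the study report.

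Neither edit requires any change to Section 9. The cost is drafting and amendment review. In the second case there is also a shift in who may enter, which the sponsor should weigh openly.
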